#### 2.5.1.3 Adverse event information

##### **Adverse event start date**

AE start date will be used for AE classification and analysis. If AE start date is not complete, then the character variable will keep the original incomplete date, the numerical date variable will be imputed and an imputation flag will indicate which date component is missing.

If AE start day is missing, and AE start month and year are not missing:

If AE start year is the same as first dose year and the AE start month is the same as the first dose month) then impute AE start day using the day of first dose. If this leads to a date after the AE end date, use AE end date instead. Otherwise (AE start year is not the same as first dose year and/or AE start month is not the same as the first dose month) impute the AE start day using the first day of the

month. If this leads to a date before informed consent, the informed consent date will be used. Imputation flag is ‘D’.

If AE start month is missing, and AE start year is not missing:

If AE start year is less than the first dose year, use the informed consent day and month. If AE start year is equal to the first dose year, use the first dose day and month. If this leads to a date after the AE end date, use AE end date instead. If AE start year is after the first dose year, use 1 January. Imputation flag is ‘M’.

If AE start year is missing:

Impute AE start date using the day of first dose. If this leads to a date after the AE end date, use AE end date instead. Imputation flag is ‘Y’.

### **Adverse event end date**

The general recommendation is not to impute AE end date. However, since AE end date will be used for AE starting date imputation, In order to carry through the logic for programming, the following intermediate step will be used. Afterwards, the original character/numeric date recorded in CRF and supportive imputed end date will be kept in the final analysis dataset.

If AE end day is missing, and AE end month and year are not missing:

Impute AE end date using the last day of the month. If this leads to a date after end of follow-up date, use end of follow-up date instead.

If AE end month is missing, and AE end year is not missing:

Impute AE end date using 31 December as the day and month. If this leads to a date after end of follow-up date, use the end of follow-up date instead.

If AE end year is missing:

Impute AE end date using the end of follow-up date.

### **Adverse event relationship and severity**

Missing AE relationship and severity will be imputed according to the rules below at the data level using “analysis” variables. The original variables will also be included in the analysis datasets.

### **Severity of adverse event**

If the severity is missing for one of the treatment emergent occurrences of an AE (the same SOC/PT), the maximal severity on the remaining occurrences will be considered. If the severity is missing for all the occurrences a “missing” category will be added in summary table.

### **Relationship to investigational product**

If the assessment of the relationship to investigational product is missing, then the relationship to investigational product has to be assumed as related and the AE considered as such in the derived analysis variable.

### **Adverse event Listings**

For date variables, only character date variables will be presented, and no imputed dates will be printed in the listings. If the AE start date is imputed, then the onset relative day will be empty; if the AE start date or end date is imputed, then AE duration will be empty.

#### 22.5.1.4 Prior and concomitant medication (other than MS treatment) date

Medication start and end date will be used for prior, concomitant and follow up medication classification and potential analysis for specific medications. In addition, the start and stop date for concomitant systemic corticosteroid will also be used to identify valid MRI scans (after a minimum of 30 days following the completion of a course of corticosteroid) for analysis, therefore different imputation rules will be used for end date of systemic corticosteroid to avoid excluding too many MRI scans (details can be found below). To keep the data integrity, if the date is not complete, then the character variable will keep the original incomplete date, the numerical date variable will be imputed (impute the end date first) and an imputation flag will indicate which date component is missing. Only the character variable will be used in data listing.

As prior and concomitant medications are flagged using the recorded start and end dates, it is not possible to apply different imputation rules based on the prior/concomitant status of a record. So the same algorithm will be used for all records made in the “prior/concomitant medication” section of the eCRF. The only distinction is made between systemic corticosteroid treatments and all other treatments. Systemic corticosteroid treatment is defined as ATC level 2 = “CORTICOSTEROIDS FOR SYSTEMIC USE”.

#### **Prior/Concomitant medication start date**

The imputation rule for concomitant medication start date is the same as AE start date.

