MRI data will only be used for analysis if not rejected or invalid, e.g. due to change of scanner, indicated as comments from the central lab.

MRIs will also be excluded from analysis if corticosteroids (ATC level 2 = “CORTICOSTEROIDS FOR SYSTEMIC USE”) were dosed within 30 days prior to the scan.

The MRI count variables (Total Number of gadolinium enhancing (Gd-enhancing) T1-lesions per MRI scan at Weeks 12 (where applicable), 24, 48, and 96, Total number of new and enlarging T2 hyperintense lesions (NELs) per MRI scan at Weeks 24, 48, and 96) will be assessed for differences between the treatment groups using negative binomial regression with an offset based on the log-transformed number of post-baseline MRI scans and covariates region, baseline EDSS strata, and corresponding baseline lesion count.

For analysis of percent brain volume change from baseline, a Mixed Model Repeated Measures (MMRM) analysis will be implemented via [REDACTED] by fitting percent change from baseline values on the cube root transformed volume from all visits after baseline in the treatment period with scheduled assessments of brain volume. The models will include factors (fixed effects) for treatment, region, baseline EDSS strata, visit, treatment-by-visit interaction, and baseline value of

the brain volume (cubic root transformed). The factor, visit, with nominal visits to avoid undue reliance on a linear in time effect will have 3 levels (Week 24, Week 48 and Week 96). An unstructured correlation matrix will be used to model the within-patient errors. Parameters will be estimated using restricted maximum likelihood method with the Newton-Raphson algorithm. Denominator degrees of freedom will be estimated using Satterthwaite's approximation.

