#### **Systemic corticosteroid medication end date**

According to the protocol, the preferred corticosteroids treatment in protocol is methylprednisolone sodium succinate 1 g, intravenously daily for 3-5 days. To avoid excluding too many MRI scans due

to the incomplete date, the end date of corticosteroid will be imputed by the date closest to 5 days after the start. Details are described as below:

If end day is missing and end month and year are not missing:

If the end month and year are the same as start date + 5, then impute the end date using start date +5; If the month and year are earlier than start date + 5, then impute the day using the last day of the month; If the month and year are later than start date + 5, then impute the day using the first day of the month. If this leads to a date after end of study follow up date, use the end of follow up date instead. Imputation flag is 'D'.

If end month is missing and year is not missing:

If the end year are the same as start date + 5, then impute the end date using start date +5; If the year are earlier than start date + 5, then impute the month and day using December 31; If the year are later than start date + 5, then impute the month and day using June 15. If this leads to a date after end of study follow up date, use the end of follow up date instead. Imputation flag is 'M'.

If end year is missing:

Impute the end date using start date +5. If this leads to a date after end of study follow up date, use the end of follow up date instead. Imputation flag is 'Y'.

A special note, for subjects with incomplete systemic corticosteroid start date, the rule of 5 days after the start would not apply for the initial imputation. Thus for these cases, after imputation of start date, the end date will be re-imputed by repeating the above rules.

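### Reusing the adverse-event start-date rule for medications can move a pre-consent steroid course to the consent date and, if its end date is also incomplete, wrongly exclude the screening MRI; the 15 June end-date branch contradicts the SAP's own principle

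*SAP*

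**What the plan says.** **Start dates.** SAP 2.5.1.4 (printed as 22.5.1.4): "The imputation rule for concomitant medication start date is the same as AE start date". The rule covers prior as well as concomitant medication: "So the same algorithm will be used for all records made in the" prior/concomitant part of the eCRF. Systemic corticosteroids get separate treatment only for the end date.

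**The borrowed rule (SAP 2.5.1.3).**
- Day missing, month other than the first-dose month: take the first of the month, but "If this leads to a date before informed consent, the informed consent date will be used". This branch has no cap at the end date.
- Month missing, recorded year earlier than that of the first dose: the day and month of consent.
- Month missing, recorded year the same as that of the first dose: the first-dose date, capped at the end date ("If AE start year is equal to the first dose year, use the first dose day and month").
- Year missing: the first-dose date, capped at the end date.

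**Steroid end dates (SAP 2.5.1.4).** The principle is that "the end date of corticosteroid will be imputed by the date closest to 5 days after the start". If only the day is missing and the recorded month is later than start + 5, the first of that month is used. If the month is missing: "If the year are later than start date + 5, then impute the month and day using June 15". Where the start was itself incomplete, the end is imputed again from the imputed start.

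**Use of these dates.** SAP 2.4.3.2 excludes an MRI if systemic corticosteroids "were dosed within 30 days prior to the scan", with no exemption for baseline. SAP 2.5.1.4 instead counts 30 days from completion of the course.

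**A separate path.** Previous MS treatments follow SAP 2.5.1.1 (the 15th, or 1 July), with no consent substitution.

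**The concern.** Adverse events are captured only from consent, so consent is a sensible lower bound for their start. Prior medications by definition may begin earlier; SAP 2.1.1 has them recorded back to 3 months before randomization. Putting such a course at consent also sits badly with eligibility, since protocol section 3.2 excludes glucocorticoid use in the 30 days before screening.

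Because the steroid end date is rebuilt from the imputed start, the error can reach the decision on scan validity. Loss of the screening scan takes the subject out of the mITT-MRI set (SAP 2.2.3), which serves the two lesion-count endpoints and brain volume. The T1 unenhancing count, the T2 count and normalized brain volume are read only at screening (SAP 2.4.3.2), so a later scheduled scan cannot stand in for it.

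The 15 June branch works against the section's stated wish not to lose too many scans: it can mark on-study scans as steroid-affected for months.

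**Working it through.** **1. Start date: the rules applied literally.** Illustrative record: steroid start May 2018 (day unknown), consent 2 July 2018, screening MRI 10 July 2018, first dose in a later month than May.

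Start: first of month = 1 May; 1 May is before 2 July; imputed start = 2 July, so start + 5 = 7 July.

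| End as recorded | Imputed end | Days from end to MRI | Result on the completion wording |
|---|---|---|---|
| 14 May 2018 | 14 May | 57 | kept, but start is after end |
| May 2018 | 31 May | 40 | kept, but start is after end |
| 2018 | 7 July | 3 | excluded |
| unknown | 7 July | 3 | excluded |

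Without the consent substitution, the last two rows give start 1 May, end 6 May, 65 days before the scan: kept. Even a five-day course begun on 31 May would have ended on 4 June, 36 days before the scan.

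An end with only the day missing can also cause a loss. True course 1 to 5 August 2018, consent 5 September, MRI 18 September, first dose 28 September; start and end both recorded as August 2018. Imputed start 5 September; the end month is earlier than start + 5, so end = 31 August, 18 days before the scan: excluded. The true gap is 44 days. Without the substitution the end is 6 August, 43 days before: kept.

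**2. How conditional this is.** Eligible five-day pre-study courses were enumerated assuming consent 14, 21 or 28 days before first dose, MRI 10 days before first dose, the course ended at least 31 days before consent and inside the 3-month look-back, and exclusion if the imputed end falls within 30 days before the scan. With only the start day missing, every course is moved to consent. Wrong exclusion of the baseline scan is then:

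| End date | Current rule | Without consent substitution |
|---|---|---|
| complete | 0% | 0% |
| day missing | 16.0% | 0% |
| month missing | 91.6% | 1.1% |
| year missing | 100% | 0% |

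With the start month missing, about 5% land on the consent date; with the start year missing, at most 0.2%. These are shares of such records under assumed timings, not expected frequencies in the trial.

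**3. End date: checking the SAP's principle.** Six of the seven sub-branches return the admissible date closest to start + 5. The exception is month missing with a later year: the closest admissible date is 1 January, and 15 June is 165 days after it (166 in a leap year).

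Start 20 December 2018, end year 2019: start + 5 = 25 December 2018, so 2019 is later.
- 15 June 2019 = start + 177 days (11 + 31 + 28 + 31 + 30 + 31 + 15).
- 1 January 2019 = start + 12 days.

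Adding the 30-day exclusion, the affected span is 177 + 30 = 207 days instead of 12 + 30 = 42. Weeks 12 and 24 are 84 days apart and Weeks 24 and 48 are 168 days apart, so 207 days can cover two scheduled post-baseline scans.

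**4. When that branch is reached.** With a known start, a five-day course ends at start + 4, which cannot fall in a later year than start + 5: 0 of 365 start dates. The shortest course that reaches it runs 26 December to 1 January and is imputed to end at start + 171 days. A true five-day course reaches it only if the start day is also missing and it crosses New Year (4 of 365 start dates): 28 December to 1 January becomes 1 December to 15 June, 196 days, against 31 days with 1 January.

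**The case against.** Several limits are fair and stand. Sites must establish that glucocorticoids stopped at least 30 days before screening, so a steroid record with no usable end date should be uncommon, and the 3-month look-back narrows the window further. SAP 2.1.1 lists corticosteroid treatment for earlier relapses under MS treatment history; a course handled as previous MS treatment follows 2.5.1.1 and escapes this problem. The scan-validity sentence in 2.5.1.4 speaks of concomitant steroids, so its reach to the baseline scan is plausible rather than explicit, although 2.4.3.2 carries no such restriction.

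On 15 June: an end year later than start + 5 shows, when the start is known, that the course lasted more than five days. A mid-year guess is then a defensible caution against keeping steroid-affected scans. It is nonetheless not the principle that the SAP states.

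A reader might also infer more than the documents support:
- **That any partly dated prior steroid costs the baseline scan.** It does not; on the completion wording the end date must be incomplete as well.
- **That the end-date rule turns ordinary five-day courses into six-month ones.** Step 4 shows that this needs an imputed start and a course crossing New Year.
- **That a lost baseline scan also removes the subject from the NEDA and SDMT models.** Both use baseline MRI counts as covariates, but the SAP does not say how a missing covariate is handled; this would follow only under complete-case fitting.
- **That a number of subjects per arm can be given.** The documents contain no count of incomplete steroid dates.

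**Conclusion.** The point holds in a narrow form. The consent substitution is unsuitable for medications lacking only the start day: it can create starts after known ends and, with an incomplete steroid end date, wrongly exclude a valid screening scan. The 15 June branch is inconsistent with the SAP's own principle and with its parallel day-missing branch.

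The size is small. Each affected baseline record costs one subject, 1/220 = 0.45% of an arm, in the MRI endpoints; each record in the 15 June branch can cost one or two scheduled scans. Few records are likely. The primary endpoint uses neither MRI validity nor medication dates, and no bias between arms is shown. The baseline part assumes that the steroid is recorded in the prior/concomitant section and that the exclusion in 2.4.3.2 applies to the screening scan as written.

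**What to change.** Three wording changes in the SAP, with matching programming specifications, before database lock:

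1. **Start date (2.5.1.4).** For medications with only the start day missing, use the first of the recorded month, or the first-dose day if that is the first-dose month; do not raise it to informed consent; never let it exceed the recorded end date. Keep the consent bound for adverse events.
2. **Steroid end date (2.5.1.4).** Replace 15 June with 1 January. The small cost is that a scan taken during a genuinely longer course could be retained.
3. **Anchor.** Use completion of the course in both 2.4.3.2 and 2.5.1.4. If the 2.4.3.2 wording were programmed on the start date, the May example with a known end of 14 May would also lose its scan, because the imputed start of 2 July is 8 days before it.

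Leave the month-missing and year-missing start branches unchanged. Setting an unknown start month to 1 January looks natural but can create the same error. With first dose 1 February 2018, MRI 20 January, and an on-study steroid recorded as start 2018 with unknown end, the present rule gives 1 February and keeps the scan. A 1 January start gives an end of 6 January, 14 days before the scan, and excludes it.

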#### **Prior/Concomitant medication end date**

Imputation of non-systemic corticosteroid medication end date

If end day is missing, and end month and year are not missing:

Impute end date using the last day of the month. If this leads to a date after end of study follow up date, use end of follow up date instead. Imputation flag is ‘D’.

If end month is missing, and end year is not missing:

Impute end date using 31 December as the day and month. If this leads to a date after end of study follow up date, use the end of follow up date instead. Imputation flag is ‘M’.

If end year is missing:

Impute date using the end of follow up date. Imputation flag is ‘Y’.

#### **Systemic corticosteroid medication end date**

According to the protocol, the preferred corticosteroids treatment in protocol is methylprednisolone sodium succinate 1 g, intravenously daily for 3-5 days. To avoid excluding too many MRI scans due

to the incomplete date, the end date of corticosteroid will be imputed by the date closest to 5 days after the start. Details are described as below:

If end day is missing and end month and year are not missing:

If the end month and year are the same as start date + 5, then impute the end date using start date +5; If the month and year are earlier than start date + 5, then impute the day using the last day of the month; If the month and year are later than start date + 5, then impute the day using the first day of the month. If this leads to a date after end of study follow up date, use the end of follow up date instead. Imputation flag is 'D'.

If end month is missing and year is not missing:

If the end year are the same as start date + 5, then impute the end date using start date +5; If the year are earlier than start date + 5, then impute the month and day using December 31; If the year are later than start date + 5, then impute the month and day using June 15. If this leads to a date after end of study follow up date, use the end of follow up date instead. Imputation flag is 'M'.

If end year is missing:

Impute the end date using start date +5. If this leads to a date after end of study follow up date, use the end of follow up date instead. Imputation flag is 'Y'.

A special note, for subjects with incomplete systemic corticosteroid start date, the rule of 5 days after the start would not apply for the initial imputation. Thus for these cases, after imputation of start date, the end date will be re-imputed by repeating the above rules.

## 2.5.2 Windows for Time Points

MRIs (including repeat imaging in case of QC rejections) are linked to specific visits, so it is not necessary to assign visits based on relative timing.

Other efficacy assessments will be summarized by the nominal visit as well and no visit window will be defined.

For safety assessments, the reference date for the derivation of relative days of events or findings will be the date of first drug intake as documented in the study medications administration page of the eCRF. All available values obtained between 2 visits including unscheduled measurements will be assigned to the appropriate visit window as specified in section 2.5.3. In the event of multiple measurements of the same test in the same window, the one closest to the targeted visit date will be used for the by-visit summary, in case of equal distance the later observation will be selected. For further details please see the section "Unscheduled Visits" as well.

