6.3.7 SAFETY DATA

Subject safety will be evaluated throughout the study during the following assessments:

- Adverse events
- Physical examination: cardiovascular system, chest and lungs, thyroid, abdomen, nervous system, skin and mucosae, and musculoskeletal system, eyes, ears, nose, mouth, throat, spine, lymph nodes, extremities, genitourinary, weight
- Hematology and differential panel: hemoglobin, hematocrit, red blood cell count, mean corpuscular hemoglobin, white blood cell count, neutrophils, lymphocytes, monocytes, eosinophils, basophils, and platelets
- Fibrinogen
- Pregnancy testing (serum or urine levels of β -human chorionic gonadotrophin (HCG)) in women of childbearing potential). In addition, pregnancy test should be conducted in case of an unexpected delay of menorrhoea
- ECG (within 2 hours pre-infusion and 60 minutes +/- 15 minutes post-infusion on days of infusion; for non-infusion days one ECG assessment should be performed)
- Blood chemistry panel: Albumin, Alkaline Phosphatase, BUN, Calcium, Chloride, Creatinine, Glucose, LDH, Magnesium, Phosphate, Potassium, SGOT (AST), SGOT (ALT), Sodium, Total Bilirubin, Total Protein, Uric Acid, and direct/ indirect bilirubin
- Liver function panel: SGOT/AST, SGPT/ALT, serum gamma-glutamyl transferase (SGGT), total bilirubin, direct/indirect bilirubin.
- Pancreatic enzyme panel: serum amylase and lipase

- Urinalysis panel for routine safety: pH, ketones, protein, glucose, blood, urobilinogen, bilirubin, microscopic sediment, specific gravity and leucocyte esterase.
- Vital signs: (within 2 hours pre-infusion and 60 minutes +/- 15 minutes post-infusion on days of infusion) systolic and diastolic blood pressure, heart rate, body temperature, and weight

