6.10 END OF STUDY FOLLOW-UP

After early termination of trial or at the end of study visit at Week 96, subjects will enter a 20-week Follow-up Period inclusive of the accelerated elimination of teriflunomide. The 11-day elimination procedure will commence at Week 100 for all subjects who completed all study visits including Week 96. For those subjects who had terminated early (discontinued or withdrawn from the study), the 11-day elimination procedure will commence the day after the Early Withdrawal from Treatment Visit. The follow up period will include visits at Weeks 100, 104, and 116. Weeks 108 and 112 will be performed via a phone call.

For subjects who withdraw their consent to participate in the study, the site should inform these subjects of the 20-week Follow-up Period inclusive of the accelerated teriflunomide elimination procedure and document this in the eCRF. Participation in the 20-week Follow-up Period inclusive of the accelerated teriflunomide elimination procedure for subjects who withdraw early is left to the discretion of the subject. If he/she elects not to participate in the 20-week Follow-up inclusive of the accelerated teriflunomide elimination procedure, after withdrawing consent and after discussion with the site, it should be documented in the eCRF.

For subjects who will participate in the 20-week Follow-up Period inclusive of the accelerated teriflunomide elimination procedure after withdrawing consent for this study, a new consent form to participate in the 20-week Follow-up Period inclusive of the accelerated teriflunomide elimination procedure will need to be signed. If he/she re-consents, the sites will complete the eCRF for Weeks 100, 104, 108, 112, and 116, accordingly.

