#### 2.1.4.5 ECG

ECG interpretation (normal/abnormal) will be collected by visit and - where applicable - time point (pre-/post-dose).

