##### **General common rules**

All safety analyses will be performed on the Safety Population as defined in Section 2.2.1, unless otherwise specified, using the following common rules:

1. For quantitative safety parameters based on central laboratory/ reading measurements, visit and treatment group will use descriptive statistics to summarize results and change from baseline values. Summaries will include the value and/or the worst value of the observation period.
2. All of the values including unscheduled measurements will be assigned to the appropriate safety analysis visit window. The safety analysis visit window is defined in Section 2.5.2. In the presence of multiple measurements of the same test in the same window, the one closest to the targeted visit date will be used for the by-visit summaries.

3. The analysis of the safety variables will in general be descriptive and no systematic statistical testing is planned.

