## 2.5.3 Unscheduled Visits

Only scheduled visit efficacy measurements will be used for analyses visit to exclude the temporary fluctuations in the clinical status that may occur with a relapse.

Safety data from unscheduled visits will be used in in all safety analyses. The unscheduled visits will be assigned to the appropriate analysis time window. The one closest to the targeted visit date will be used in the presence of multiple measurements within the same time window. If two observations

within a window have the same target distance, the later one will be used for analysis. The following windows will be used:

Week of study	Target day	Minimal days	Maximum days
1 (day 1)	1	1	1
1 (day 2)	2	2	4
2	8	5	11
3	15	12	21
4	28	22	42
8	56	43	70
12	84	71	98
16	112	99	126
20	140	127	154
24	168	155	210
36	252	211	294
48	336	295	378
60	420	379	462
72	504	463	546
84	588	547	630
96	672	631	686
100	700	687	714
104	728	715	770
116	812	771	

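### Vital signs have no pre-/post-infusion time point in the SAP, so its tie rule selects the post-infusion reading for by-visit summaries at Weeks 3, 24, 48 and 72 wherever both readings are recorded

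*SAP*

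**What the plan says.** **What is collected.** Protocol 6.3.7 sets the timing of vital signs as "within 2 hours pre-infusion and 60 minutes +/- 15 minutes post-infusion on days of infusion) systolic and diastolic blood pressure", followed by the remaining parameters. Section 7.5.3 names five infusion days: Week 1 Day 1, Week 3 Day 15, and Weeks 24, 48 and 72.

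**How a value is chosen.** The common rules in SAP 2.4.5 state: "All of the values including unscheduled measurements will be assigned to the appropriate safety analysis visit window". SAP 2.5.2 repeats this ("All available values obtained between 2 visits including unscheduled measurements will be assigned to the appropriate visit window as specified in section 2.5.3"), takes the value nearest the target date for the by-visit summary, and adds that "in case of equal distance the later observation will be selected". SAP 2.5.3 says the same of two observations that "within a window have the same target distance, the later one will be used for analysis".

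**How vital signs are summarised.** SAP 2.1.4.3 lists the parameters and gives no time point. SAP 2.4.5.3 asks for summary statistics of raw values and changes from baseline at each visit, and for plots of mean change over time. Under SAP 2.1.4, baseline is the last value before the first dose.

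**The contrast.** For ECG, SAP 2.1.4.5 collects the interpretation by visit and, where applicable, "time point (pre-/post-dose", and SAP 2.4.5.5 tabulates it that way.

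**The concern.** A reading taken about an hour after an infusion is a different quantity from an ordinary visit reading. Protocol 4.4 expects that hypotension may occur with the infusion, and 7.2.1.1 lists infusion related reaction as very common with ublituximab. If the tie rule quietly selects the post-infusion reading, the by-visit series mixes two quantities under one label. Over Weeks 24 to 84 the series would alternate between them: infusion visits at 24, 48 and 72, ordinary visits at 36, 60 and 84.

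Hypertension is a listed common reaction for both drugs (Protocol 7.1.1.2 and 7.2.1.2), so readers will look to these tables and plots for a sustained blood-pressure effect. At four visits they would see that effect plus whatever the infusion itself did. The pre-infusion reading, which is the like-for-like comparator of the baseline, would be left out of the by-visit display.

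**Working it through.** The plan gives no figure for this point, so there is none to reproduce. The check applies the stated rule to the stated schedule.

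**1. Selection rule.** For a reading on study day d in a window with target day t, the distance is |d − t|. The smallest distance is kept; if equal, the later reading. The targets in SAP 2.5.3 are whole days.

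**2. Same-day pair.** The pre- and post-infusion readings share d, so their distances are identical whatever the visit timing, and the later one, post-infusion, is chosen. With the ±5-day allowance that Protocol Tables 5 to 7 (footnote 4) give from Week 8 on:

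| Visit | Target t | Days d tested | Distance, pre = post | Selected |
|---|---|---|---|---|
| Week 1 Day 1 | 1 | 1 | 0 | post |
| Week 3 | 15 | 15 | 0 | post |
| Week 24 | 168 | 163, 168, 173 | 5, 0, 5 | post |
| Week 48 | 336 | 331, 336, 341 | 5, 0, 5 | post |
| Week 72 | 504 | 499, 504, 509 | 5, 0, 5 | post |

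That is 1 + 1 + 3 + 3 + 3 = 11 cases, with the post-infusion reading selected in all 11. The pair could be displaced only by a reading from another day that lies nearer the target.

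**3. Day 1 is a special case.** The pre-infusion reading on Day 1 is normally the baseline itself, so its change from baseline is zero by definition. Selecting the post-infusion value there does no harm. The visits that matter are Weeks 3, 24, 48 and 72.

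**4. Share of visits.** Scheduled vital-sign visits after Day 1:
- Table 5: Week 1 Day 2, Week 2, Week 3, and Weeks 4, 8, 12, 16 and 20, which is 8.
- Table 6: Weeks 24, 36, 48, 60, 72 and 84, which is 6.
- Table 7: Weeks 96, 100, 104 and 116, which is 4 (Weeks 108 and 112 are phone calls).

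8 + 6 + 4 = 18, which matches the 19 SAP windows less Day 1. Four of 18 (22%) are infusion visits.

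**5. What the summary then measures.** For one subject at an infusion visit:

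post − baseline = (pre − baseline) + (post − pre)

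The within-arm mean change therefore includes the mean acute infusion change δ = mean(post − pre). The between-arm contrast includes δ(ublituximab) − δ(teriflunomide), which is zero only if the infusion changes the reading equally in both arms. The documents give no value for δ, so the shift cannot be put in mmHg.

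**6. Displays that do not depend on the selection (SAP 2.4.5.3).** These are the incidence of abnormal vital signs at any time in the observation period, the shift from baseline to worst status, and the full-profile listing of subjects with an abnormal observation.

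**The case against.** **The second reading may not be recorded.** Footnote 13, attached to the vital signs row of Protocol Tables 5 and 6, places those assessments before each infusion. Appendix F lists vital signs only among the pre-infusion items. The footnote with pre- and post-infusion timing (footnote 9) belongs to ECG. On that schedule there is no tie, and the SAP's different handling of ECG and vital signs is consistent. This stands as a condition on the point: it applies wherever both readings are recorded. It does not remove the point, because 6.3.7 requires both explicitly, and the Version 5.0 change list mentions pre- and post-infusion windows for vital signs as well as ECG.

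**Only descriptive displays are touched.** This stands in full. No systematic testing of safety variables is planned (SAP 2.4.5), and the displays in step 6 use all readings.

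**The design is double-dummy.** Both arms receive an infusion and the same premedication at the same visits, so the arms are compared at matched times. This largely stands. It does not guarantee equal δ, since one arm receives active antibody and the other placebo, and it does nothing for the within-arm trend over visits.

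**The pre-infusion reading is not a pure resting value either.** It may follow premedication, and investigators are asked to consider withholding antihypertensives beforehand. That is true, but the baseline reading, where it is taken on Day 1 before the infusion, is obtained under the same conditions. Pre-infusion against baseline is therefore like for like.

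**A stronger reading concerns early leavers.** SAP 2.5.2 says that "the reference date for the derivation of relative days of events or findings will be the date of first drug intake", and no window ends at last dose. A reader might infer that follow-up values of subjects who stop early are wrongly tabulated as on-treatment, and that windows should close 30 days after last dose. The documents do not support that.
- The windows are headed by week of study, not by treatment status, and SAP 2.4.5 deliberately runs the observation period to 20 weeks after last dose.
- No day offsets are given for early leavers. Borrowing the Week 96 spacing as an assumption (700 − 672 = 28, 728 − 672 = 56, 812 − 672 = 140), a stop on Day 170 puts readings on Days 226 and 310 in the Week 36 and Week 48 windows. If that subject was infused on Day 168, these are 226 − 168 = 58 and 310 − 168 = 142 days after the infusion. Both lie inside the 24-week (168-day) interval between later infusions.
- The elimination procedure in Protocol 6.10.1 is directed at teriflunomide only.

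A 30-day cut would therefore relabel values within the antibody's planned dosing interval. It is a debatable choice, not a correction.

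**Conclusion.** The point holds within limits. Where both readings are recorded as Protocol 6.3.7 requires, the SAP's rules place the post-infusion vital signs in the by-visit summaries and mean-change plots at Weeks 3, 24, 48 and 72. That is 4 of 18 scheduled vital-sign visits after Day 1. They are compared with a pre-dose baseline, while the other 14 visits show ordinary readings. The by-visit series is then not one quantity over time.

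A reader might infer that a safety signal is hidden or that the arm comparison is biased. Neither follows. Abnormality incidence, worst-value shifts and the listings keep every reading, and the arms share the same infusion and premedication schedule. The size of any distortion depends on δ, and between arms on its difference, and the documents quantify neither.

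The conclusion rests on two assumptions: that post-infusion vital signs are in fact recorded, on which the protocol contradicts itself, and that no reading from another day lies nearer the target. The early-leaver matter is optional at most.

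**What to change.** Amend the SAP before database lock and unblinding:

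- **2.1.4.3 and 2.4.5.3:** on infusion days, summarise vital signs by visit and time point (pre-infusion, post-infusion), as already planned for ECG. Use the pre-infusion value for by-visit change from baseline and for the mean-change plots at visits after Day 1. Tabulate post- minus pre-infusion change separately for all five infusions, including Day 1.
- **2.5.2 (and the matching sentence in 2.5.3):** apply the nearest-to-target and later-if-tied rules within time point, so that the two readings no longer compete.
- **Protocol 6.3.7 against footnote 13 of Tables 5 and 6 and Appendix F:** reconcile these passages on whether post-infusion vital signs are recorded, and state the outcome in the SAP.
- **Optional:** flag values taken after last dose in the by-visit safety tables. Do not add a 30-day cut-off.

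The cost is SAP wording and table programming. No new data are needed, provided each reading in the eCRF carries a time point or clock time; the documents do not show the form, so this should be checked.
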